Diabetic foot ulceration (DFU) is a common and largely preventable complication. [1] While most of these ulcers can be treated successfully, some will persist and become infected. Ultimately, nearly one fifth of patients with infected lower-extremity diabetic ulcers will require amputation of the affected limb, resulting in staggering costs for both the patient and the healthcare system. Prevention by identifying people at higher risk is the key for better clinical management of such patients. It is not uncommon for patients suffering from diabetes to have concomitant lower extremity edema or even venous insufficiency[2-4] and they subsequently may benefit from graduated compression[5-7]. However, because of the common association of peripheral arterial disease (PAD) in patients with diabetes[8-10], most clinicians are reluctant to apply compressive dressings in fear of exacerbating the symptoms of PAD and the possible resulting gangrene[11].

Unfortunately, this area has received comparatively little attention from industry, academia, or insurance providers. A novel micro-mobile intermittent pneumatic foot compression device (AVEX Footbeat, Inc.) offers alternative means providing lower extremity compression. This device is portable and can be used in ambulatory settings providing increased venous blood and relief from concomitant lower extremity edema.

Section D: Purpose and Objectives

The purpose of this study is to conduct an observational study with N=30 patients to assess whether this micro-mobile foot compression device can help reduce lower extremity in patients with both diabetes and lower extremity edema without compromising the vascular supply.

The main purpose of this study is to determine if the device lessens edema. This study will also evaluate a new research device to see if it may help prevent diabetic foot ulcers. Additionally, it may potentially help delay progression of foot disease and produce a better quality of life by providing a better blood flow to foot and ankle.

Primary Endpoints: Reduction in lower extremity edema at 4 weeks of continuous device usage. Peripheral edema will be measured at baseline, 48 hours, 1 week and 4 weeks. Peripheral edema will be directly measured by traditional volume change assessment and indirectly by skin perfusion pressure assessment.

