Secondary Endpoints: 1) Improvement in balance and fall risk as measured at baseline and 4 weeks. 2) 48 Hours of continuous daily physical activity using a validated body worn sensor as measured at baseline and 4 weeks. 3) Gait assessment at baseline and 4 weeks.

Specific Aim and Hypothesis

Aim 1. To assess the effectiveness of a micro-mobile foot compression device that provides mild compression to help reduce peripheral edema as compared to baseline in patients with both diabetes and lower extremity edema in a four-week observational clinical trial of 30 patients.

Hypothesis 1: The micro-mobile foot compression device will result in edema reduction when compared to baseline peripheral edema for the study population.

Aim 2. To assess the effect of micro-mobile foot compression device on the macro and micro lower extremity circulation as measured by Ankle Brachial Index (ABI) and Skin Perfusion Pressure (SPP) Measurements.

Hypothesis 2: The micro-mobile foot compression device will help improve macro and micro- circulation in the lower extremity of patients with diabetes and lower extremity edema as compared to baseline. We expect to see positive changes in ABI and SPP measurements.

Aim 3. To assess the effect micro-mobile foot compression device on the quality of life quantified using the validated, international quality of life assessment survey SF12, fear of falling quantified by FES-I, and risk of falling assessment quantified by gait, balance and spontaneous daily physical activity of patients with diabetes and lower extremity edema.

Hypothesis 3. The micro-mobile foot compression device will improve the quality of life, lower the risk of falling, lower fear of falling, and improve activity level of patients as compared to baseline assessments.

Section E: Protocol Risks/Subjects

E1. Risk Category

Category 2: Research involving greater than minimal risk, but presenting the prospect of direct benefit to the individual subjects.

E2. Subjects

Gender:

Both

Age:

Adult (18-64 yrs), Geriatric (65+ yrs)

Ethnicity:

All Ethnicities

Primary Language:

English, Spanish

Groups to be recruited will include:

Patients

Which if any of the following vulnerable populations will be recruited as subjects?

Vulnerable populations require special protections. How will you obtain informed consent, protect subject confidentiality, and prevent undue coercion?

E3. Pregnant woman/fetus

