Additionally, skin perfusion pressure (SPP) monitor will be used to assess vascular status for all patients. SPP offers a non-invasive and real-time assessment of critical limb ischemia. It indicates the pressure at which blood flow resumes in capillaries. SPP is unaffected by falsely elevated systolic blood pressures, calcified arteries and peripheral edema. Typically SPP readings are obtained by photoplethysmography (cuff occlusion and re-appearance of pulsatile blood flux) or laser Doppler (cuff occlusion/thermal hyperemia and movement of red blood cells).

Edema Assessment – Peripheral edema will be assessed at baseline, using clinical signs and circumference measurements at foot, calf and ankles or via volumetric water displacement.

Physical Performance Tests - Balance assessment: Balance will be quantified using validated body worn sensors (BalanSens™, Biosensics LLC, USA). The system measures ankle and hip motion in three dimensions (3D), 2D COM sway as well as RCI in ML and AP directions [16]. Balance will be assessed according to Romberg protocol during eyes-open and eyes-closed condition during double, semi-tandem, and full tandem stances (see the attached list of questionnaires/assessments for further explanation).

Physical Performance Tests - Gait assessment: Gait performance will be assessed using by a validated body worn sensors (LegSys™, Biosensics LLC, USA) [17-19]. The device uses five sensor modules respectively attached to right and left anterior shins, right and left anterior thighs, and posteriorly to the lower back. Based on the subject's height and using a two-link inverse pendulum model the following spatio-temporal gait parameters will be estimated: velocity, stride length, stride time, double support, single support, stride-to-stride variability, and gait initiation [20]. In addition, the COM range of motion during walking will be calculated by using the data from the sensor attached to lower-back. Gait will be assessed over a distance of 20 meters under 4 conditions: (1) walking at habitual speed (single task); (2) walking at habitual speed while counting backward from a random number (e.g. 83) (dual task); (3) walking at maximum speed (fast walking), (4) Timed Up and Go (TUG); and (5) alternative 8 step test

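### Section D counts skin perfusion pressure as an indirect measure of the primary edema endpoint, which no other section supports, and the direct edema method is not held constant

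*Combined protocol and SAP*

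**What the plan says.** Section D states the overall purpose as reducing edema "without compromising the vascular supply", which treats edema and circulation as two things. Its Primary Endpoints paragraph then joins them: "Peripheral edema will be directly measured by traditional volume change assessment and indirectly by skin perfusion pressure assessment".

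Aim 2 concerns "macro and micro lower extremity circulation as measured by Ankle Brachial Index (ABI) and Skin Perfusion Pressure (SPP) Measurements", and Hypothesis 2 adds: "We expect to see positive changes in ABI and SPP measurements".

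In F2, the "skin perfusion pressure (SPP) monitor will be used to assess vascular status for all patients". The same paragraph explains the reading ("It indicates the pressure at which blood flow resumes in capillaries") and adds: "SPP is unaffected by falsely elevated systolic blood pressures, calcified arteries and peripheral edema". The separate Edema Assessment paragraph does not mention SPP. It lists clinical signs and "circumference measurements at foot, calf and ankles or via volumetric water displacement".

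G2 tests Hypothesis 1 with ANOVA and Fisher's exact test on a within-subject rate of edema reduction, and identifies the outcome only as one described earlier. It adds a paired t-test on the amount of edema reduction at study end. A later regression has five named predictors of edema reduction, one of which is SPP. For Hypothesis 2, the change in SPP is a dependent variable.

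**The concern.** Reducing edema is the stated main purpose and the subject of Hypothesis 1. If Section D is followed as written, a change in SPP counts as evidence on edema, although Hypothesis 2 already expects SPP to rise as a circulation effect. One measurement would then inform two hypotheses that the protocol presents as distinct. Section D also does not say which direction or size of SPP change would mean less edema.

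The direct measure has its own gap. The endpoint names volume change, but the procedures permit another method, so volume is not assured for every patient. G1 says the pilot's results will be used to size a larger superiority trial. That calculation needs the mean change and the variability of one identified variable, measured in one way.

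**Working it through.** The plan gives no alpha, power, effect size or standard deviation for this endpoint, so there is no figure to reproduce. The check sets the sections side by side.

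**1. Role of SPP wherever it is mentioned**

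| Place | Role given to SPP |
|---|---|
| Section D, Primary Endpoints | Indirect measure of edema |
| Aim 2 and Hypothesis 2 | Circulation outcome, with ABI |
| F2, vascular paragraphs | Vascular status; unaffected by edema |
| G2 | Predictor of edema reduction (Hypothesis 1 regression); dependent variable (Hypothesis 2) |

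One of four places treats SPP as an edema measure. The F2 paragraph on edema assessment, where such a role would be expected, omits it.

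**2. The F2 statement that SPP is unaffected by edema.** Two readings are possible. Taken literally, SPP does not respond to edema and cannot track it. On the milder reading, edema does not distort the SPP value. The milder reading is plausible because edema is listed beside falsely high systolic pressure and calcified arteries, which are sources of measurement error. Neither reading supports using an SPP change as evidence of edema reduction.

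**3. The variable tested for Hypothesis 1.** G2's back-reference leads to the Section D endpoint definition, which includes SPP. G2's own use of SPP as a predictor of edema reduction, and as a Hypothesis 2 outcome, points the other way. G2 does not say which applies.

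**4. Candidates for that variable.** Volume gives 1, circumference gives 3 (foot, calf, ankles) and SPP gives 1: 1 + 3 + 1 = 5 numeric candidates, with clinical signs in addition. Four of the five come from the open choice of direct method and one from the SPP clause. The Visit 4 text in F2 asks for assessments similar to those at baseline. It does not require the same edema method in the same patient.

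**5. Overlap in the regression.** The predictors are activity, BMI, ABI, SPP and the device, so SPP is 1 of 5. SPP would be on both sides of the model only if two conditions both held: SPP is part of the outcome, and the predictor is the same SPP quantity. G2 does not say whether the predictor is baseline SPP or its change. If either condition fails, the same quantity is not on both sides.

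**6. Fit of the named tests.** A paired t-test suits a continuous change from baseline. Fisher's exact test needs categories, and the plan defines no category of edema response.

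**The case against.** The strongest reply is that the plan already separates the roles. Section D ranks the measures by calling one direct and the other indirect. G2 uses SPP as a predictor and as a Hypothesis 2 outcome, and the amount of edema reduction in the paired t-test most naturally means the direct measure. On this view only one loose clause remains, in a proof-of-concept pilot with no success criterion, and both kinds of measurement are collected anyway.

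Much of this stands. G2 does lean towards SPP being outside the Hypothesis 1 outcome. But calling a measure indirect does not make it supportive, and the clause sits inside the primary endpoint definition with nothing to rank or combine the two. An endpoint should not have to be inferred from a list of predictors. It is also fair that the circumference-or-displacement question is separate and would remain without the SPP clause, and that the limb to be analysed is not stated.

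Four stronger readings are tempting but not supported:

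- A reader might infer that F2 flatly contradicts Section D. The milder reading of F2 prevents that conclusion.
- A reader might infer that SPP alone could decide Hypothesis 1. The plan contains no such rule.
- A reader might infer an inflated false-positive rate, for example 1 − 0.95² = 0.0975 for two independent tests at 0.05. That assumes an alpha and an either-may-count rule, and the documents give neither.
- A reader might infer that the regression certainly has SPP on both sides. That needs both conditions in step 5 of the working.

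**Conclusion.** The point holds as a conflict of definition and should be fixed. Section D gives SPP an edema role that Aim 2, Hypothesis 2, F2 and G2 do not support, and G2's back-reference leads to that definition while its own use of SPP points away from it. Independently, the direct edema method is not held constant across patients or visits.

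The size is limited to what the text shows: one of four places, and at least five numeric candidates for the Hypothesis 1 outcome. No effect on power, bias or false positives is claimed. The conclusion does not depend on how the F2 statement about edema is read, nor on the regression overlap being real. Confidence is high that the sections mismatch. How far this would alter the Hypothesis 1 result cannot be derived from the documents.

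**What to change.** - **Section D:** remove SPP from the primary edema endpoint and keep it as a Hypothesis 2 outcome. Labelling it supportive would also end the conflict over its rank, but the plan would then have to say what SPP change means less edema, and nothing in it provides a basis for that.
- **F2, Edema Assessment, and G2:** define the Hypothesis 1 outcome as the change from baseline to 4 weeks in one direct edema measure, taken by the same method in every patient at every visit where edema is measured. Section D already names volume. The other F2 method becomes supportive. State the limb analysed.
- **G2:** replace the back-reference with that named variable and make the paired t-test on it the primary Hypothesis 1 analysis. Keep Fisher's exact test only if a categorical edema response is defined in advance. State whether the SPP predictor is the baseline value or the change.

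The cost is wording. No new type of measurement is added, and SPP is still collected. The small downside is that the two F2 methods are no longer interchangeable for the primary outcome, so the chosen one must be available wherever edema is assessed. That may include the two senior centers that J2 names as offering assessment space.

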Will pregnant women and/or fetuses (as described in 45 CFR 46 Subpart B) be enrolled in the research?

No

E4. Neonates

Will neonates of uncertain viability or nonviable neonates (as described in 45 CFR 46 Subpart B) be enrolled in the research?

No

E5. Children

Will children be enrolled in the research?

No

Section F: Design/Procedure

F1. Design

Select one category that most adequately describes your research:

c) Pilot

Discuss the research design including but not limited to such issues as: probability of group assignment, potential for subject to be randomized to placebo group, use of control subjects, etc.

In this proof of concept, intent to treat trial, 30 consecutive patients with diabetes and lower extremity edema will be recruited from the outpatient clinic at Baylor College of Medicine. Patients will be consented per the local Institutional Review Board's guidelines and approval for this study.

Inclusion Criteria:

a) Males or females age 18-90 years old with history of type 1 or 2 diabetes and the ability and willingness to provide Informed consent b) Patients at risk of developing diabetic foot ulcers c) Patient is willing to participate in all procedures and follow up evaluations necessary to complete the study. d) Patients who have undergone lower extremity surgery / amputation may be enrolled into the study at the clinical judgment of the Investigator

Exclusion Criteria:

a) Patients with severe peripheral vascular disease (ABI or ankle brachial systolic pressure index <0.5) b) Patients with diabetic foot ulcers in the plantar foot region c) Patients with active wound infection, or untreated osteomyelitis d) Patients currently on immunosuppressive drugs. e) Pregnant or breastfeeding females. (standard urine pregnancy done on women during physical exam procedures) f) Acute fractures of the foot g) Acute heart failure h) Participation in an interventional Study within the last 30 days i) Non-ambulatory or unable to stand without help or walk a distance of at least 6 feet without assistance. k) Patients with major foot amputation. j) Patients who are unable or unwilling to participate in all procedures and follow up evaluations h) Patients with major foot deformities which won't fit in the diabetic shoes

F2. Procedure

Following is a summary of study procedures:

Study Day 0 (initiation), Visit 1 The following baseline values will be assessed and documented.

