Upper Extremity Test: Investigators will measure arm motion from each participant by implementing a validated technology based on wearable sensor system named LegSys. This system will assess respectively spatio-temporal parameters of arm motion in a clinical setting. The LegSys system will be used with 2 sensors to capture arm motion, one placed at the subject's wrist and another at their elbow. While being at a comfortable position, the subject will be asked to flex and extend their arm for 20 seconds at a fast speed. Subject will also be asked to repeat this task but counting backwards as they flex and extend their arm (dual task). We may also add wrist weights (no more than 5 pounds) to increase the resistance of this task.

Objective assessment of physical activity: Spontaneous daily physical activities as well as the risk of falling during activity of daily living are quantified using a validated body worn sensor named PAMSys™ (Biosensics, LLC, USA). PAMSys is a small long-term recording movement sensor which is unobtrusively inserted into a comfortable shirt (PAMshirt™). The system contains inertial sensors with software developed to identify postural positions and movements such as walking, standing, sitting, or lying during a measuring period of 48 hr. It has proven to be sensitive (87–99%) and specific (87–99.7%)[21, 22] for postural position and detection of walking in different samples of older adults and patient groups.

Plantar Pressure Assessment: Plantar pressure will be examined using computerized pressure insoles® (Fscan®, TekScan, Boston, MA). Subjects will be asked to walk a distance of approximately 20 feet at habitual speed while wearing regular shoes with and without AVEX insoles.

Assessment of user friendliness, acceptability, and perception of need: We will use a questionnaire tailored to the topic of this study to evaluate the perception of the target population in receiving benefit from the proposed technology. Subjects are asked to answer the questionnaire at the end of study. The questionnaire includes 11 items and allows assessing how target population perceives the need of such technology in management of their problem.

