Other assessments: Other relevant assessments are Demographic/Health questionnaire, the Mini-Metal State Exam, the mobility-tiredness scale, Barthel Index, Depression Scale, fear of falling (Short-Falls Efficacy Scale – International)[25], quality of life (SF-12 Health Survey)[26], Fried Frailty Criteria, Foot Questionnaire, Pain Assessment, Fall Log and Contact Agreement, Physical activity log, follow-up questionnaire, and Shoe-fit test

AVEX insole: The AVEX insole will be given to the subject. The research personnel will adjust the clutching reel (BOA technology) in order to ensure a comfortable shoe fit. The research personnel will also provide device education to the subject and will answer any questions which may arise.

Study Day 1, Visit 2 48-hour follow up: All participants will be asked to return to clinic approximately 48 hours after visit 1. In this visit, (1) any adverse events will be assessed; (2) activity measurement (body sensor) will be returned; (3) AVEX insole data will be downloaded to ensure operability and patient compliance; and (4) further device education will be provided in case any issues have risen

Study Day 2, Visit 3 1-week follow-up: All participants will be asked to return to clinic approximately 1 week after visit 1. In this visit, (1) any adverse events will be assessed; and (2) AVEX data download to ensure operability and patient compliance. Device education will be provided if needed. The subject will be asked to return the device at their next visit. Similar assessments performed during visit 1 may be performed again during this visit.

Study Day 3, Visit 4 4-week follow-up: All participants will be asked to return to clinic approximately 4 weeks after visit 1. In this visit, outcome assessment using similar assessments described for Study Day 0 will be performed. In addition, benefit and user-friendliness of the AVEX insoles and Boa Technology 'Clutch Reel' will be assessed using a questionnaire. The subject will return the device back to the research personnel.

Patients will be asked to wear a comfortable shirt which holds a small activity monitor (PAMSys) for a period of 48 Hours (2 days). Patients will be requested to return this device via a pre-paid FEDEX envelope

Study Day 4, Visit 5 Three month follow-up: All participants will be contacted by the study coordinator approximately three months post the last study visit (Visit 4) to document potential incident of diabetic foot ulcer or falls.

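### The baseline 48-hour activity recording very likely runs during early insole use, and the week-4 recording probably follows insole return; both windows need stating and reconciling

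*Combined protocol and SAP*

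**What the plan says.** Section D (Secondary Endpoints) asks for 48 hours of body-worn sensor activity at baseline and at 4 weeks, and Hypothesis 3 expects improvement on baseline. F2 then sets out the visits.

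- **Visit 1.** The list opens "Study Day 0 (initiation), Visit 1 The following baseline values will be assessed and documented". It includes the PAMSys activity monitor, which records "during a measuring period of 48 hr" and also measures fall risk in daily living. The list ends with the insole: "The AVEX insole will be given to the subject".
- **Visit 2, about 48 hours later.** "2) activity measurement (body sensor) will be returned; (3) AVEX insole data will be downloaded to ensure operability and patient compliance".
- **Visit 3, about 1 week.** After the insole download and education: "The subject will be asked to return the device at their next visit".
- **Visit 4, about 4 weeks.** "outcome assessment using similar assessments described for Study Day 0 will be performed", and at the end of the visit "The subject will return the device back to the research personnel".
- **Next paragraph, no visit named.** "Patients will be asked to wear a comfortable shirt which holds a small activity monitor (PAMSys) for a period of 48 Hours (2 days)", with the monitor sent back by pre-paid courier. The entry after it is the three-month contact.

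In G2, the Hypothesis 3 analysis is a multivariate ANOVA on steps, walking and standing time, walking bouts, postural transitions and SF12. Activity level is also a predictor in the Hypothesis 1 and Hypothesis 2 regressions, with no recording named.

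**The concern.** A before-after activity endpoint needs a first recording without the device and a second one on it. The visit sequence appears to give the reverse: device on at the start, probably device off at the end. The measured change would then not be the effect of 4 weeks of use. It could be too small, reversed, or, if the new insole lowers activity at first, too large.

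The activity secondary endpoint, the daily-living fall-risk measure and the Hypothesis 3 sensor variables rest on this contrast. The joint Hypothesis 3 test is affected too, because SF12 shares the same multivariate model, although SF12 scores themselves are not. G1 says that the results will be used to size a larger trial, so a distorted activity estimate could carry forward. A window that was not recorded cannot be recovered at analysis.

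**Working it through.** The plan gives no figure to reproduce here. The check sets the timings side by side and then asks what the contrast estimates.

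**First window.** The recording lasts 48 hours, is listed at Visit 1 and ends with sensor return at Visit 2, about 48 hours later. The insole is issued at Visit 1, and its compliance data are read at Visit 2, which presupposes use in between. Section D supports this. The primary endpoint is at 4 weeks of continuous use and Visit 4 falls 4 weeks after Visit 1, so use has to start at about Visit 1. F2 describes no period without the insole. Taking both starts at Visit 1, the overlap is 48 of 48 hours. Neither start time is stated, so this is very likely rather than certain.

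**Second window.** Visit 4 is at about 4 × 7 × 24 = 672 hours, and the insole is returned there. If the monitor is put on at or after that visit, the recording runs from about 672 to 720 hours, and the overlap with insole use is 0 of 48 hours. If the undated paragraph is instead a general instruction for every recording, its courier return conflicts with the clinic return at Visit 2, and the week-4 window has no timing at all.

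**What the contrast estimates.** Let B be activity without the insole and D the change in activity after 4 weeks of use. Let a be the share of D already present in the first 48 hours of use, and c the share remaining in the 48 hours after return.

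- Visits as they read: (B + cD) − (B + aD) = (c − a)D
- Only the first window made device-free: (B + cD) − B = cD
- Only the second window moved on-device: (B + D) − (B + aD) = (1 − a)D
- Both corrected: (B + D) − B = D

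The documents give neither a nor c. The values below are assumptions, with a from −0.5 to 0.5 and c from 0 to 1. A negative a would mean that early discomfort, a risk named in Section H1, lowers activity. Entries are multiples of D; with both windows corrected the entry is always 1.00.

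| a | c | As the visits read | First window only | Second window only |
|---|---|---|---|---|
| 0 | 1 | 1.00 | 1.00 | 1.00 |
| 0 | 0.5 | 0.50 | 0.50 | 1.00 |
| 0.25 | 0.5 | 0.25 | 0.50 | 0.75 |
| 0.5 | 0.5 | 0 | 0.50 | 0.50 |
| 0.5 | 0 | −0.50 | 0 | 0.50 |
| −0.25 | 0.75 | 1.00 | 0.75 | 1.25 |
| −0.5 | 1 | 1.50 | 1.00 | 1.50 |

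Over these ranges the contrast runs from −0.5 to 1.5 times D. It equals D only when c − a = 1; for a and c both between 0 and 1, that means a = 0 and c = 1. Moving only the second window leaves an error of −aD. When a is negative, that is further from D than the sequence as it reads whenever 0 < 1 − c < 2|a|; the row a = −0.25, c = 0.75 is an example.

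**The case against.** The second window is inferred. The monitor paragraph names no visit and no start time, and paragraph order is weak evidence because F2 soon runs on into consent wording addressed to the participant. The attached assessment list and some pages are not in the text available for review and might give the timing. This stands: the second window is probable, not established. It does not remove the problem, because the alternative reading conflicts with the Visit 2 return.

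The reach is also limited. This is a secondary endpoint in an uncontrolled pilot with no power target. That stands too.

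Three stronger readings are tempting and not supported:

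- **That the payment terms confirm a recording after Visit 4.** Section L pays $30 per visit up to $120, which is four visits. This fits an unpaid three-month contact and says nothing about when the sensor is worn.
- **That a bias or loss of power can be quoted.** The effect, its variability, a and c are all absent from the documents. A one-variable power figure would also not describe the multivariate Hypothesis 3 test.
- **That moving the week-4 recording is enough.** The algebra shows that, made alone, this step can increase the error.

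**Conclusion.** The point holds as a timing fault that should be fixed, with medium confidence. The first window is the better supported: the baseline recording very likely lies within insole use. The second probably lies after insole return and is otherwise undefined. Followed in that order, the activity change does not measure what Section D defines, except in the special case c − a = 1. Its bias has no computable size or direction; the −0.5 to 1.5 range rests wholly on assumed values of a and c.

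A reader might infer that the activity endpoint certainly fails to compare baseline with 4 weeks of use. The text does not go that far, because no start time is stated for either recording. The primary edema measurement, SF12 scores, FES-I and in-clinic gait and balance are untouched. The activity-level predictor in the Hypothesis 1 and Hypothesis 2 regressions is affected, since its source recording is unnamed. Even with both windows corrected, this remains an uncontrolled before-after comparison.

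**What to change.** Make changes 1 and 2 together.

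1. **First window.** State in F2 when the recording starts relative to insole use, and reconcile this with Section D. Either complete it before insole use begins, or stop calling it baseline and restate the endpoint and Hypothesis 3 as change from the first 48 hours of use to the last 48 hours before Visit 4. The second option must say that there is no device-free baseline and that the result is (1 − a)D: too low if a > 0, too high if a < 0. The choice is the sponsor's.
2. **Second window.** Schedule it for the last 48 hours before Visit 4 with the insole still in use. Issue the sensor at Visit 3 or by mail, collect it at Visit 4, record start and stop times, and move the recording if the visit moves. Report any recording after insole return separately, as off-device.
3. **G2.** Name the recording that supplies activity level in the Hypothesis 1 and Hypothesis 2 regressions.

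**Cost.** Relabelling and change 3 are text only. Change 2 uses the same sensor and adds no visit, but it needs a patient reminder and an unsupervised start, with some risk of failed or mistimed recordings. If issued at Visit 3, the sensor is out for about 3 weeks. A recording before insole use costs more. Consent must precede any screening procedure and Visit 1 is the first visit, so it needs an earlier consented contact or a change in hand-out timing. Changing the hand-out timing would also affect the Visit 2 insole download and the 48-hour edema measurement.
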